6.2.2 Timing of Study Interventions

Treatment cycles for this study are 21 days each cycle. All study interventions will begin after all predose study procedures and assessments have been completed, as detailed in Section 1.3. Every effort should be made to begin the first dose of study intervention on the day of randomization; however, if this is not achieved, study intervention is to be initiated no later than 3 days from the date of randomization. All subsequent cycles of study intervention may be administered up to 3 days before or 3 days after the scheduled day due to administrative reasons per the investigator's judgment.

The reason for any variability in the administration of the study intervention(s) outside of the protocol-specified windows is to be documented in the participant's chart and recorded in the eCRFs.

6.2.2.1 Timing for Administration for MK-1454

MK-1454 will be administered as an IT injection on Day 1, Day 8, and Day 15 of the first 2 cycles (Q1W for Cycles 1 and 2), then on Day 1 of every 21-day cycle (Q3W) from Cycle 3 onward.

On days when both MK-1454 and pembrolizumab are to be administered, MK-1454 will be administered within 0.5 to 4 h after completion of the pembrolizumab IV infusion.

6.2.2.2 Timing for Administration of Pembrolizumab

Pembrolizumab will be administered as an IV infusion on Day 1 of each 21-day cycle after all predose study procedures and assessments have been completed, as detailed in Section 1.3.

The Pembrolizumab Pharmacy Manual contains specific instructions for dose preparation and administration.

6.2.3 Handling, Storage, and Accountability

The investigator or designee must confirm appropriate temperature conditions have been maintained during transit for all study intervention received, and any discrepancies are reported and resolved before use of the study intervention.

Only participants enrolled in the study may receive study intervention, and only authorized site staff may supply or administer study intervention. All study interventions must be stored in a secure, environmentally controlled, and monitored (manual or automated) area in accordance with the labeled storage conditions with access limited to the investigator and authorized site staff.

The investigator, institution, or the head of the medical institution (where applicable) is responsible for study intervention accountability, reconciliation, and record maintenance (ie, receipt, reconciliation, and final disposition records).

For all study sites, the local country Sponsor personnel or designee will provide appropriate documentation that must be completed for drug accountability and return, or local discard and destruction if appropriate. Where local discard and destruction is appropriate, the investigator is responsible for ensuring that a local discard/destruction procedure is documented.

The study site is responsible for recording the lot number, manufacturer, and expiry date for any locally purchased product (if applicable) as per local guidelines unless otherwise instructed by the Sponsor.

The investigator shall take responsibility for and shall take all steps to maintain appropriate records and ensure appropriate supply, storage, handling, distribution, and usage of study interventions in accordance with the protocol and any applicable laws and regulations.

6.3 Measures to Minimize Bias: Randomization and Blinding

6.3.1 Intervention Assignment

Intervention allocation will occur centrally using an IRT. There are 2 intervention arms. Participants will be randomized to 1 of 2 intervention arms: MK-1454 in combination with pembrolizumab (Arm 1) or pembrolizumab monotherapy (Arm 2).

6.3.2 Stratification

Intervention randomization will be stratified according to the following factors:

1. PD-L1 status (CPS ≥ 1 to < 20 vs CPS ≥ 20)
2. ECOG performance status (0 vs 1)
3. HPV status (positive vs negative): HPV status for oropharynx cancer is determined by p16 IHC (positive vs negative); HPV status for participants without oropharynx cancer (eg, cancers of the oral cavity, hypopharynx and larynx) is considered HPV-negative.

6.3.3 Blinding

This is an open-label study; therefore, the Sponsor, investigator, and participant will know the intervention administered.

6.4 Study Intervention Compliance

Interruptions from the protocol-specified treatment plan for > 12 weeks between MK-1454 or pembrolizumab doses for non drug-related or administrative reasons require consultation between the investigator and the Sponsor and written documentation of the collaborative decision on participant management.

6.5 Concomitant Therapy

Medications specifically prohibited in the exclusion criteria are not allowed during the ongoing study. If there is a clinical indication for any medication specifically prohibited, discontinuation from study intervention may be required. The investigator should discuss any questions regarding this with the Sponsor. The final decision on any supportive therapy rests with the investigator and/or the participant's primary physician. However, the decision to continue the participant on study intervention requires the mutual agreement of the investigator, the Sponsor, and the participant.

6.5.1 Acceptable Concomitant Medications

All treatments that the investigator considers necessary for a participant's welfare may be administered, at the discretion of the investigator, in keeping with the community standards of medical care except for those that are prohibited, as described in Section 6.5.2. All concomitant medication will be recorded in the eCRF including all prescription, OTC, herbal supplements, and IV medications and fluids. If changes occur during the study period, documentation of drug dosage, frequency, route, and date may also be included in the eCRF.

All concomitant medications received within 30 days before the first dose of study intervention and up to 30 days after the last dose of study intervention should be recorded. Concomitant medications administered after 30 days after the last dose of study intervention should be recorded for SAEs and ECIs as defined in Section 8.4.

6.5.2 Prohibited Concomitant Medications

Participants are prohibited from receiving the following therapies during the Screening and Treatment Phases (including retreatment for post-CR relapse) of this study:

- Antineoplastic systemic chemotherapy or biological therapy
- Immunotherapy not specified in this protocol
- Chemotherapy not specified in this protocol
- Investigational agents other than pembrolizumab or MK-1454
- Radiation therapy

Note: Radiation therapy to a symptomatic solitary lesion or to the brain may be considered on an exceptional case-by-case basis after consultation with Sponsor. The participant must have clear measurable disease outside the radiated field. Administration of palliative radiation therapy will be considered clinical progression for the purposes of determining PFS.

- Live vaccines within 30 days prior to the first dose of study intervention and while participating in the study. Examples of live vaccines include, but are not limited to the following: measles, mumps, rubella, varicella/zoster, yellow fever, rabies, BCG, and typhoid vaccine. Seasonal influenza vaccines for injection are generally killed virus vaccines and are allowed; however, intranasal influenza vaccines (eg, FluMist[®]) are live attenuated vaccines and are not allowed.
- Systemic glucocorticoids for any purpose other than to modulate symptoms from an AE of suspected immunologic etiology. The use of physiologic doses of corticosteroids may be approved after consultation with the Sponsor.

Participants who, in the assessment of the investigator, require the use of any of the aforementioned treatments for clinical management should be removed from the study. Participants may receive other medications that the investigator deems to be medically necessary.

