9 STATISTICAL ANALYSIS PLAN

This section outlines the statistical analysis strategies and procedures for the primary and secondary analyses of the study. Exploratory and other nonconfirmatory analyses will be outlined in a separate sSAP.

If, after the study has begun, changes are made to primary and/or secondary objectives, or the statistical methods related to those objectives, then the protocol will be amended (consistent with ICH Guideline E9). Changes to exploratory or other nonconfirmatory analyses made after the protocol has been finalized, but prior to the conduct of any analyses, will be documented in the sSAP as needed and referenced in the CSR for the study. ^{CCI}

CCI

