9.4 Analysis Endpoints

9.4.1 Efficacy/Immunogenicity/Pharmacokinetics Endpoints

Primary Efficacy Endpoint

- OR: a confirmed CR or PR per RECIST 1.1 based on BICR. ORR is the proportion of participants with objective response.

Secondary Efficacy Endpoints

- PFS: time from randomization to the first documented PD per RECIST 1.1 based on BICR or death from any cause, whichever occurs first. See Section 9.6.1 for the definition of censoring.
- DOR: time from the first documented evidence of CR or PR until PD per RECIST 1.1 as assessed by BICR or death due to any cause, whichever occurs first, in participants demonstrating CR or PR.
- OS: time from randomization to the date of death due to any cause.

CCI

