9.6.1.2 Progression-free Survival

The nonparametric Kaplan-Meier method [Kaplan, E. L. 1958] will be used to estimate the PFS curve for each treatment group in participants with CPS ≥ 1 and in participants with CPS ≥ 20 . The treatment difference in PFS will be assessed by the stratified log-rank test. A stratified Cox proportional hazard model [Cox, D. R. 1972] with Efron's method [Efron, B. 1977] of tie handling will be used to assess the magnitude of the treatment difference (ie, the HR) between the treatment arms. The HR and its 95% CI from the stratified Cox model with Efron's method of tie handling and with a single treatment covariate will be reported. The stratification factor used for randomization (Section 6.3.2) will be applied to both the stratified log-rank test and the stratified Cox model.

Because disease progression is assessed periodically, PD can occur any time in the interval between the last assessment when PD is not documented and the assessment when PD is documented. For the primary analysis, for participants with PD, the true date of disease progression will be approximated by the date of the first assessment at which PD is objectively documented per RECIST 1.1, based on BICR. Death is always considered as a confirmed PD event. Participants who do not experience a PFS event will be censored at the last disease assessment. Sensitivity analyses will be performed for comparison of PFS based on the investigator's assessment.

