In order to evaluate the robustness of the PFS endpoint per RECIST 1.1 by BICR, 1 primary and 2 sensitivity analyses with a different set of censoring rules will be performed. For the primary analysis, if the events (PD or death) are immediately after more than 1 missed disease assessment, the data are censored at the last disease assessment prior to the missed visits. Also, data after new anticancer therapy are censored at the last disease assessment prior to the initiation of new anticancer therapy. The first sensitivity analysis follows the ITT principle. That is, PDs/deaths are counted as events regardless of missed study visits or initiation of new anticancer therapy. The second sensitivity analysis considers initiation of new anticancer treatment or discontinuation of treatment due to reasons other than CR to be a PD event for participants without documented PD or death. If a participant meets multiple criteria for censoring, the censoring criterion that occurs earliest will be applied. The censoring rules for primary and sensitivity analyses are summarized in [Table 11](#).

In case there is an imbalance between the treatment groups on disease assessment schedules or censoring patterns, we may also perform a sensitivity analysis for PFS using interval censored data [Finkelstein, D. M. 1986], which modifies the Cox proportional hazard model for interval censored data. The interval will be constructed so that the left endpoint is the date of the last disease assessment without documented PD and the right endpoint is the date of documented PD or death, whichever occurs earlier.

Table 11 Censoring Rules for Primary and Sensitivity Analyses of PFS

Situation	Primary Analysis	Sensitivity Analysis 1	Sensitivity Analysis 2
PD or death documented after ≤ 1 missed disease assessment, and before new anticancer therapy, if any	Progressed at date of documented PD or death	Progressed at date of documented PD or death	Progressed at date of documented PD or death
PD or death documented immediately after ≥ 2 consecutive missed disease assessments or after new anticancer therapy, if any	Censored at last disease assessment prior to the earlier date of ≥ 2 consecutive missed disease assessments and new anticancer therapy, if any	Progressed at date of documented PD or death	Progressed at date of documented PD or death

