No PD and no death; new anticancer treatment is not initiated	Censored at last disease assessment	Censored at last disease assessment	Progressed at treatment discontinuation due to reasons other than CR; otherwise censored at last disease assessment if participant is still receiving study treatment or has completed study treatment
No PD and no death; new anticancer treatment is initiated	Censored at last disease assessment before new anticancer treatment	Censored at last disease assessment	Progressed at date of new anticancer treatment
PD progressive disease; PFS progression free survival.			

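### Section 6.5.2 makes palliative radiotherapy a progression for PFS, while Section 9 counts only BICR-assessed PD or death in the primary PFS analysis (minor; the passages must be reconciled)

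*Combined protocol and SAP*

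**What the plan says.** Section 6.5.2 prohibits radiotherapy during screening and treatment. It allows an exception, case by case and after consultation with the Sponsor, for a symptomatic solitary lesion or the brain. It then adds: "Administration of palliative radiation therapy will be considered clinical progression for the purposes of determining PFS". The sentence does not say which PFS analysis it means.

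Section 9 opens: "This section outlines the statistical analysis strategies and procedures for the primary and secondary analyses of the study". Section 9.4.1 defines PFS as "time from randomization to the first documented PD per RECIST 1.1 based on BICR or death from any cause, whichever occurs first". Section 9.6.1.2 dates progression in the primary analysis at "the date of the first assessment at which PD is objectively documented per RECIST 1.1, based on BICR". On later treatment it says: "Also, data after new anticancer therapy are censored at the last disease assessment prior to the initiation of new anticancer therapy". For a participant with neither PD nor death who starts new treatment, the primary column of Table 11 reads "Censored at last disease assessment before new anticancer treatment". Under Sensitivity Analysis 1, "PDs/deaths are counted as events regardless of missed study visits or initiation of new anticancer therapy". Under Sensitivity Analysis 2, such a participant counts as progressed on the date of the new treatment. No row of Table 11 mentions radiotherapy or clinical progression.

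**The concern.** The two parts of the document give different PFS events for the same participant. Section 4.2 explains that the trial is unblinded and that BICR is there to reduce bias in ORR and PFS. Section 4.2.3.1 rests the final determination of radiologic progression on central rather than local reading. Under the 6.5.2 sentence, a decision to irradiate would be a PFS event with no central reading behind it. That decision is taken by a site that knows the arm, in consultation with a Sponsor that also knows it (Section 6.3.3). If irradiation were used or timed differently by arm, the PFS comparison would shift for reasons that BICR cannot correct.

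A secondary gap lies behind this. Table 11 turns on new anticancer therapy, and the visible text does not say whether palliative radiotherapy is one. The same term ends imaging in Sections 8.2.3, 8.2.4 and 8.10.3.2, so it also affects which scans exist.

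**Working it through.** No figure in the plan depends on this point, so there is none to reproduce. The check is a comparison of rules, followed by an illustration of size.

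**Rules applied to one participant.** Scans fall every 6 weeks in the first year. Suppose palliative radiotherapy is given between the week 12 and week 18 scans, with no PD by BICR up to week 12 and BICR PD at week 18.

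| Rule | Result |
|---|---|
| Section 6.5.2 | Event at radiotherapy |
| Table 11 primary, radiotherapy is new anticancer therapy | Censored at week 12 |
| Table 11 primary, radiotherapy is not new anticancer therapy | Event at week 18 |
| Sensitivity Analysis 1 | Event at week 18, if that scan is taken |
| Sensitivity Analysis 2 | Event at week 18; if no PD or death were ever documented and radiotherapy is new anticancer therapy, event at its start |

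Neither primary reading reproduces the 6.5.2 result. Only Sensitivity Analysis 2 can place an event at the start of new treatment, and only where no PD or death is documented.

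**Size, closed form.** Assume constant cause-specific hazards. Let q1 and q2 be the shares of first events in Arm 1 and Arm 2 that are radiotherapy before BICR PD or death. The total hazard in an arm is then its PD-or-death hazard divided by (1 − q), so

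HR(radiotherapy as event) = HR(radiotherapy censored) × (1 − q2)/(1 − q1).

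The shares are assumptions. With HR(censored) = 1.00:
- 5% and 5%: 0.95/0.95 = 1.00
- 2% and 5%: 0.95/0.98 = 0.97

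**Size, simulation.** Assumptions: 200,000 participants per arm; exponential PFS with a control median of 3.5 months; 15% of events are deaths; PD dated at the next scheduled scan; 24-month cut-off; true HR 1. Each cell gives the HR with radiotherapy as an event / censored at the last scan / ignored.

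| Irradiated, Arm 1 vs Arm 2 | Unrelated to progression | In the 6 weeks before progression or death |
|---|---|---|
| 2% vs 5% | 0.97 / 1.00 / 1.00 | 0.99 / 1.03 / 1.00 |

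With balanced use of 2%, 5% or 10% in both arms, the three rules differ by at most 0.005. At 2% versus 5% the largest gap is about 0.03 before rounding. Control medians of 2.5 and 6 months change these gaps by less than 0.01. For scale, 100 per arm gives about 195 to 198 PFS events, so the standard deviation of log HR is about √(4/196) = 0.14.

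No rule is best throughout. The event rule is biased when radiotherapy is unrelated to progression, and censoring is biased when radiotherapy shortly precedes it.

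**The case against.** The strongest reply is that Section 9 governs. It sets the methods for secondary endpoints, and Table 13 sends PFS to Table 11, so the 6.5.2 sentence is a stray line that no analyst would follow. Radiotherapy is described as exceptional, and PFS carries no hypothesis. The 6.5.2 sentence names neither BICR nor primary PFS, so it could be meant for Sensitivity Analysis 2 or for the planned investigator-assessed PFS. Most of this stands, and it is why the point is minor. It does not make the sentence right: as written, it applies to PFS without limit.

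A reader might infer three equally open outcomes for every irradiated participant. The documents do not support that. Section 8.1.5.2 says that starting another anticancer therapy should lead to discontinuation of study intervention and a move to survival follow-up, whereas Section 6.5.3 contemplates radiotherapy with study intervention possibly continuing. Read together, they suggest that palliative radiotherapy is not new anticancer therapy when study intervention continues. This is an inference, not a definition. Data-entry guidance or the supplemental SAP, neither of which is visible, may settle it, and parts of Section 9 are redacted.

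A reader might also infer that the censored and ignored readings coincide once a participant leaves, because Section 6.5.2 says that participants who "require the use of any of the aforementioned treatments for clinical management should be removed from the study". They do not coincide. A death after at most one missed assessment is a primary event if radiotherapy is not new anticancer therapy, and is censored if it is. That difference needs no later scan.

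**Conclusion.** The conflict between Section 6.5.2 and Section 9 is real and rests on readable text. It is minor. Section 9 is the likely governing text, and it already defines the primary PFS event as BICR PD or death. The undefined status of radiotherapy is a secondary matter of missing detail, held with less confidence because other study documents may resolve it.

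The size is hypothetical: essentially nil with balanced use, and about 0.03 in the HR at an assumed 2% versus 5%, against sampling variation of 0.14 in log HR. A reader might infer a material threat to the PFS result. A gap of about 0.12 needs an assumed split such as 5% versus 15%, which is implausible when 6.5.2 calls radiotherapy exceptional, and no rate in the documents supports it. Nor does the point reach the primary conclusion: ORR testing, its alpha and the sample size are untouched.

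**What to change.** 1. Delete the PFS sentence from Section 6.5.2, or confine it to Sensitivity Analysis 2 or the investigator-assessed PFS analysis. The primary PFS event then stays BICR PD or death, as Section 9 has it. If the sentence moves to Sensitivity Analysis 2, state whether radiotherapy counts as an event even when PD or death is documented later, because that analysis currently uses the later date.
2. As a consistency edit, add a footnote to Tables 11 and 12 saying whether on-study palliative radiotherapy counts as new anticancer therapy. Use the same meaning in Sections 8.2.3, 8.2.4 and 8.10.3.2, where imaging ends. The choice is the sponsor's and should be fixed before the data are analysed.

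The cost is one sentence deleted or moved and one footnote repeated. Sample size, alpha and ORR testing do not change, and no change to the clinical use of radiotherapy is implied.

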7 DISCONTINUATION OF STUDY INTERVENTION AND PARTICIPANT WITHDRAWAL

7.1 Discontinuation of Study Intervention

Discontinuation of study intervention does not represent withdrawal from the study.

As certain data on clinical events beyond study intervention discontinuation may be important to the study, they must be collected through the participant's last scheduled follow-up, even if the participant has discontinued study intervention. Therefore, all participants who discontinue study intervention prior to completion of the protocol-specified treatment period will still continue to participate in the study as specified in Section 1.3 and Section 8.1.9, or if available, Protocol Clarification Letter.

Participants may discontinue study intervention at any time for any reason or be discontinued from the study intervention at the discretion of the investigator should any untoward effect occur. In addition, a participant may be discontinued from study intervention by the investigator or the Sponsor if study intervention is inappropriate, the study plan is violated, or for administrative and/or other safety reasons. Specific details regarding procedures to be performed at study intervention discontinuation are provided in Section 8.1.9.

A participant must be discontinued from study intervention but continue to be monitored in the study for any of the following reasons:

- The participant or participant's legally acceptable representative requests to discontinue study intervention.
- The participant interrupts study intervention administration for more than 12 consecutive weeks.
- The participant has a medical condition or personal circumstance which, in the opinion of the investigator and/or Sponsor, placed the participant at unnecessary risk from continued administration of study intervention.
- The participant has a confirmed positive serum pregnancy test.
- Confirmed radiographic disease progression outlined in Section 8.2 (exception if the Sponsor approves treatment continuation).
- Progression or recurrence of any malignancy, or any occurrence of another malignancy that requires active treatment.
- Any study-intervention-related toxicity specified as a reason for permanent discontinuation in the guidelines for dose modification due to AEs in Section 6.6.
- Intercurrent illness other than another malignancy, as noted above, that prevents further administration of treatment.
- Investigator's decision to discontinue treatment.

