7.2 Participant Withdrawal From the Study

A participant must be withdrawn from the study if the participant or participant's legally acceptable representative withdraws consent from the study.

If a participant withdraws from the study, they will no longer receive study intervention or be followed at scheduled protocol visits.

Specific details regarding procedures to be performed at the time of withdrawal from the study, as well as specific details regarding withdrawal from FBR, are outlined in Section 8.1.9. The procedures to be performed should a participant repeatedly fail to return for scheduled visits and/or if the study site is unable to contact the participant are outlined in Section 7.3.

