8.1.5.2 Concomitant Medications

The investigator or qualified designee will record medication, if any, taken by the participant during the study.

All medications related to reportable SAEs and ECIs should be recorded, as defined in Section 8.4.

All new anticancer therapy initiated after the study start must be recorded in the eCRF. If a participant initiates another anticancer therapy other than the assigned study intervention(s), the study intervention(s) should be discontinued, and the participant will move into the Survival Follow-up Phase. If a participant initiates a new anticancer therapy within 30 days after the last dose of the study intervention, the 30-day Safety Follow-up Visit is to occur before administration of the first dose of the new therapy.

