8.1.9 Discontinuation and Withdrawal

Participants who discontinue study intervention prior to completion of the treatment period should be encouraged to continue to be followed for all remaining study visits as outlined in the SoA and Section 8.10.3.

When a participant withdraws from participation in the study, all applicable activities scheduled for the End of Treatment/Discontinuation visit should be performed (at the time of withdrawal). Any AEs that are present at the time of withdrawal should be followed in accordance with the safety requirements outlined in Section 8.4.3.

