8.10.3.3 Survival Follow-up Visits

Participants who experience confirmed PD or start a new anticancer therapy will move into the Survival Follow-up Phase and should be contacted by telephone every 12 weeks to assess for survival status until death, withdrawal of consent, or the end of the study, whichever occurs first.

The Sponsor may request survival status be assessed at additional time points during the course of the study. For example, these additional time points may be requested prior to but not limited to an efficacy IA for internal decision-making and/or final analysis. All participants who are not known to have died prior to the request for these additional survival status time points will be contacted at that time.

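### Section 6.5.2 removes participants who need a prohibited treatment from the study, which for randomized participants contradicts the protocol's own follow-up rules

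*Combined protocol and SAP*

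**What the plan says.** Section 6.5.2 lists treatments prohibited during the screening and treatment phases: other systemic anticancer drugs, immunotherapy, investigational agents, radiation, live vaccines and systemic glucocorticoids, with some exceptions. It ends by saying that participants who, in the investigator's assessment, "require the use of any of the aforementioned treatments for clinical management should be removed from the study".

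Other sections read differently:

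- Section 6.5, the parent section: "If there is a clinical indication for any medication specifically prohibited, discontinuation from study intervention may be required". It names study intervention, not the study.
- Section 7.1: "Discontinuation of study intervention does not represent withdrawal from the study". Those who stop early continue to take part.
- Section 7.2 gives withdrawal of consent as the trigger for leaving the study, and states the effect: "If a participant withdraws from the study, they will no longer receive study intervention or be followed at scheduled protocol visits".
- Section 8.1.9: participants who stop intervention early "should be encouraged to continue to be followed for all remaining study visits as outlined in the SoA and Section 8.10.3".
- Section 8.1.5.2: if another anticancer therapy is started, "the study intervention(s) should be discontinued, and the participant will move into the Survival Follow-up Phase".
- Section 8.10.3.3: participants with confirmed progression or a new anticancer therapy "will move into the Survival Follow-up Phase and should be contacted by telephone every 12 weeks". It adds: "The Sponsor may request survival status be assessed at additional time points during the course of the study".
- The synopsis (Section 1.1) follows all participants by telephone for OS until death, withdrawn consent or study end.
- Sections 8.10.3.2 and 4.1 continue imaging after intervention stops without progression. A new anticancer treatment ends it; a live vaccine or a steroid is not among the listed stops.

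**The concern.** The protocol separates stopping treatment from leaving the study, and gives leaving the study a concrete effect: scheduled follow-up ends. Section 6.5.2 uses the language of leaving the study for an event that elsewhere leads only to a change of follow-up phase or to continued imaging. No section says which text prevails. A site that looks up a prohibited drug finds an instruction to remove, with no pointer to Section 7.1 or 8.10.3.

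At stake is the completeness of follow-up in the ITT population (Section 9.5.1: all randomized participants). The trigger is an investigator's view of clinical need in an open-label trial, so loss of follow-up through this route need not be unrelated to prognosis or to arm.

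**Working it through.** No arithmetic applies. The check sets the passages side by side for each type of participant and follows the result into the analysis rules.

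1. **Still in screening.** Nobody has been randomized, so removal is a screen failure (Section 5.4). There is no conflict.

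2. **Randomized, trigger is a new anticancer therapy.** Section 6.5.2 says leave the study. Sections 8.1.5.2 and 8.10.3.3 say survival follow-up, and the synopsis and Section 7.1 agree. The conflict over survival contact is direct. There is none over imaging, because Sections 8.2.3 and 8.10.3.2 end imaging at a new anticancer treatment by design.

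3. **Randomized, no progression, trigger is not anticancer therapy** (a live vaccine, or a systemic steroid outside the exceptions). Section 6.5.2 says leave the study. Section 7.1 and the synopsis keep the participant in follow-up, and Sections 8.10.3.2 and 4.1 keep imaging going if intervention stops. The conflict covers both survival contact and imaging.

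4. **Softer support.** Section 7.2 lists only withdrawal of consent but does not say that the list is exhaustive. Section 8.1.9 encourages attendance and does not require it. Both point the same way as Section 7.1; neither is a flat contradiction of 6.5.2.

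5. **Effect on OS.** Section 9.6.1.3 censors participants without a documented death at the last known contact. If survival calls stop at removal, OS is censored there and a later death may go unrecorded.

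6. **Effect on PFS.** The primary PFS analysis already censors before new anticancer therapy (Section 9.6.1.2, Table 11), so removal for that reason does not change it. Sensitivity Analysis 1 does count later progression and death, and deaths after removal could be missed. For the triggers in step 3, stopping imaging would leave PFS censored at the last assessment.

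7. **Effect on ORR.** A response must be confirmed at least 4 weeks after it is first seen (Section 8.2.3), and missing data count as nonresponse (Table 13). Section 8.2.4 asks for a scan at discontinuation, within a window of 4 weeks either side, unless one was done in the previous 4 weeks. Section 8.1.9 asks for the applicable end-of-treatment activities even at withdrawal. If the first response is at least 4 weeks old with no scan since, the discontinuation scan can serve as confirmation. If it is less than 4 weeks old, a further scan is not mandatory and one done that day would be too early. So a response is at risk only when it was first seen less than 4 weeks before a trigger of the kind in step 3 and imaging then stops.

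8. **Size.** A size would need the number removed, their arm and the timing. The documents give none of these.

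**The case against.** The strongest reply is that the sentence is loose wording for removal from study intervention. Section 8.3.4.2 is similarly loose: it excludes or discontinues participants from the study on a positive pregnancy test, whereas Section 7.1 lists a confirmed positive serum test as a reason to stop intervention while monitoring continues. The intent may well be as this reply says. But the second example repeats the conflict and does not cure it, and Section 7.1 draws exactly the distinction that 6.5.2 blurs.

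The second reply is that few participants are touched. Section 6.5.2 stops at the end of the treatment phase, so later-line therapy after confirmed progression and treatment discontinuation lies outside it. Steroids for immune-related events are exempt, physiologic doses may be approved, and Sections 6.5.2 and 6.5.3 allow radiation in some cases. For new anticancer therapy, Sections 8.1.5.2 and 8.10.3.3 state the destination specifically. All of this stands, and it limits the severity.

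The third reply is that the consequences are modest. OS is secondary, has no hypothesis, and carries only nominal p-values (Section 9.6.1). The affected PFS analysis is a sensitivity analysis. The Sponsor can ask for survival status, and everyone not known to have died is then contacted. This also stands, except that such requests are optional and so are a backstop, not a rule.

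**Conclusion.** The inconsistency is real and the text is wrong as written for randomized participants. It is direct against Sections 7.1, 8.1.5.2 and 8.10.3.3 and the synopsis, and against Sections 8.10.3.2 and 4.1 when the trigger is not anticancer therapy and there is no progression. Severity is minor to moderate. The consequences assume that a site follows 6.5.2 literally.

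Three stronger readings are tempting and are not supported:

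- A reader might infer a general threat to the primary endpoint. The scan at discontinuation in Section 8.2.4 and the end-of-treatment activities in Section 8.1.9 confine it to the narrow case in step 7.
- A reader might convert each lost response into percentage points of ORR using 100 or 50 per arm. Those denominators are not fixed: the 50 rests on an assumed 50% prevalence of CPS ≥20 (Section 9.9), and the List of Tables shows a scenario with 130 participants in total. Without a number affected, the conversion says nothing about importance.
- A reader might infer a bias in OS of known direction. Censoring could be informative, but nothing in the documents gives its frequency or its split by arm.

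**What to change.** Split the last instruction of Section 6.5.2 in two. Limit removal from the study to participants not yet randomized. State that randomized participants who require a listed treatment remain in the study for survival follow-up under Section 8.10.3.3 and the synopsis and, where Section 8.10.3.2 applies, for imaging. Reconcile the similar wording in Section 8.3.4.2, and its country-specific counterpart in Appendix 7, with Section 7.1 at the same time.

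Whether study intervention stops or continues in these situations is a clinical rule for the sponsor to reconcile across Sections 6.5, 6.5.2 and 6.5.3; no position is taken here.

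The cost is a wording change. It adds no visits or procedures, because the 12-weekly calls and the follow-up imaging are already planned.
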